3.2. STUDIED DEVICE

The studied device, Pocket-X Gel, manufactured by Israeli-based Tree of Life Pharma Ltd., is an *in-situ* gelling device, used as physical barrier against bacterial re-colonization of the periodontal pockets following root surface debridement or scaling and root planing. Pocket-X Gel is provided in a pre-filled syringe along with 2 tips. It is applied to the periodontal pocket by a dentist using the provided syringe bearing one of the tips. It is applied in the form of a liquid, which transforms into a gel once placed in the periodontal pocket, due to contact with body temperature. The gel fills the periodontal pocket and prevents bacterial infiltration into the pre-cleaned pocket. One syringe can be used for multiple periodontal pockets present in the mouth of the same patient. The syringe or tip cannot be used on a different patient.

Pocket-X Gel contains the following components: Water, Poloxamer 407, Hyaluronic Acid, Phenoxyethanol, Octenidine Dihydrochloride.

The device is biodegradable. It remains within the periodontal pocket for a period of 1-3 weeks, afterwards it is either degraded or ejected from the pocket following natural sealing of the pocket as part of the gums healing process.

Pocket-X Gel only contains materials that are commonly used in oral products and are considered safe for oral use based on available literature. Additionally, *in-vivo* animal experiments conducted with the product at a GLP-certified laboratory indicated no irritation or sensitization. It is therefore expected that treatment with Pocket-X Gel will present a high safety profile during the study.

Furthermore, the product's application in the form of a liquid and its transformation into a gel only after its application allows to the product to perfectly fit the pocket's dimensions and shape. In addition, the product is applied through a thin and flexible plastic tip that does not traumatize the surrounding tissues. It is therefore expected that the product and its administration process will cause no discomfort to the patient.

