4. OBJECTIVES

The overall objective of this study is to assess the safety and efficacy of Pocket-X Gel in the improvement of gingival healing and natural sealing of periodontal pockets in patients with periodontal disease, following scaling and root planing. Safety will be evaluated in accordance with the adverse events reported by participants and oral pathologies recorded by the investigators, compared between segments treated with the studied device and segments untreated with the studied device (in case of localized adverse events) and to adverse events attributed to scaling and root planing based on available literature. Efficacy will be determined in respect to the differences between the measurements taken from segments treated with the studied device and segments that were not treated with the studied device, also taking into account efficacy measurements from similar studies and studies on scaling and root planing, based on available literature.

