9.2. SAFETY ASSESSMENT

Safety assessment will be conducted based on adverse events reported by the study participants as well as any new pathologies observed by the investigators during visits that did not exist at baseline or have worsened since baseline. Such observations will also be regarded as adverse events.

Safety assessment will be conducted by analyzing the adverse events, their quantity, severity, duration and their connection to the studied device. In case that the adverse event is localized, these parameters will be compared between the segment(s) treated with Pocket-X Gel and the untreated segments of the same patient. Adverse events will also be compared to adverse events reported during scaling and root planing studies, based on available literature.

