15. STATISTICAL ANALYSIS

15.1. SAMPLE SIZE CONSIDERATION

The rationale for sample size was based on demonstrating a difference in change in pocket depth between the tested segments and the control, reflecting effect size of 0.5 with 80% power and 5% significance level.

Effect size is defined as the difference in change between the treatments adjusted to standard deviation, and calculated as follows:

$$\frac{(\text{Change from baseline in Test segments} - \text{Change from baseline in Control segments})}{\text{Common standard deviation of the change}}$$

Sample size Justification *

A sample size of 27 will have 80% power to detect an effect size of 0.5 using a Paired t-test with a 0.05 one-sided significance level.

Assuming ~20% dropout rate, 34 subjects will be recruited, in order to have 27 participants who complete the study.

Reference:

* Additional sample size justification presents the same sample size and effect size, but specifies the expected changes within each treatment and the common standard deviation:

A sample size of 27 will have 80% power to detect a difference in means of -0.5 (e.g. a First condition mean, μ_1 , of 2.0 and a Second condition mean, μ_2 , of 2.5), assuming a standard deviation of differences of 1.0, using a paired T-test with a 0.05 one-sided significance level.

The calculations are summarized in the table below:

	1	2
Test significance level, α	0.05	0.05
1 or 2 sided test?	1	1
First condition mean, μ_1	2.0	
Second condition mean, μ_2	2.5	
Mean difference, $\mu_d = \mu_1 - \mu_2$	-0.5	
Standard deviation of differences, σ_d	1.0	
Effect size, $\delta = \mu_d / \sigma_d$	0.5	0.5
Power (%)	80	80
N	27	27

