15.2. STATISTICAL METHODS

Study Population:

Intent-to-treat (ITT) population – all patients enrolled to the study who received at least one treatment.

Per Protocol (PP) population - all patients in the ITT population who completed the study according to the protocol and with no major protocol violations.

General

All measured variables and derived parameters will be listed individually and, if appropriate, tabulated by descriptive statistics. For categorical variables, summary tables will be provided giving sample size, absolute and relative frequency and 95% CI (Confidence Interval) for proportions by study arm. For continuous variables, summary tables will be provided giving sample size, arithmetic mean, standard deviation, median, minimum and maximum and 95% CI (Confidence Interval) by study arm for means of variables.

All tests will be two-tailed, and a p-value of 5% or less will be considered statistically significant.

The data will be analyzed using the SAS ® version 9.3 (SAS Institute, Cary North Carolina).

Periodontal pockets treated with Pocket-X Gel will be analyzed vs.control pockets.

Efficacy assessment

The following efficacy parameters will be summarized in appropriate tables by treatment and visit. Changes from baseline will be summarized as well.

- Pocket probing depth
- Bleeding index
- Recession level
- Clinical attachment level
- Mobility grade
- Furcation
- Specific periodontal bacteria quantification [optional]

The Paired T-test or Signed rank test for two means (paired observations) (as is appropriate) will be applied for analyzing the calculated changes by time point within each treatment.

The Paired T-test or Signed rank test for two means (paired observations) (as is appropriate) will be applied for analyzing the difference in the above measurements and changes between the treatments.

Responder will be defined based on improvement of gingival healing and natural sealing of periodontal pockets. Chi-square test or Fisher's Exact test (as is appropriate) will be applied for comparing the proportion of responders between the tested and the control segments.

The efficacy results will be compared also to literature data, if available. The two-sample T-test or Non-parametric Wilcoxon-Mann-Whitney Rank sum test for independent samples (as is appropriate) will be applied for comparative analysis.

Safety assessment

Safety assessments will be based on Adverse Events (AEs) and oral inspections recorded at each visit.

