All AEs will be coded using coding dictionaries MedDRA (most updated version) and will be

summarized by system organ class (SOC) and preferred term (PT).

AEs will be listed individually including SOC, PT, seriousness of event, onset and resolution dates, duration, severity, relationship to the study treatment, action taken and outcome.

Frequency AEs and treatment-related adverse events will be summarized in tables by SOC, PT and treatment and by seriousness.

In case that the adverse event is localized, frequency of local AEs will be compared between the segment(s) treated with Pocket-X Geland the untreated segments of the same patient using Chi-square test or Fisher's Exact test (as is appropriate).

Adverse events will also be compared to adverse events reported during scaling and root planing studies, based on available literature. Chi-square test or Fisher's Exact test (as is appropriate) will be used for comparison in incidence of events.

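### The within-mouth comparison of local adverse events has only a low-powered 5% test and no interval for the gel-minus-control difference; a paired-difference confidence interval should carry the safety statement

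*Combined protocol and SAP*

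**What the plan says.** Section 4 makes safety a joint aim with efficacy: "The overall objective of this study is to assess the safety and efficacy of Pocket-X Gel". It names two comparators for adverse events. One is internal, with events "compared between segments treated with the studied device and segments untreated with the studied device (in case of localized adverse events". The other is external: "to adverse events attributed to scaling and root planing based on available literature".

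The safety part of section 15.2 implements the internal comparison: "In case that the adverse event is localized, frequency of local AEs will be compared between the segment(s) treated with Pocket-X" Gel and the same patient's untreated segments, using chi-square or Fisher's exact test as appropriate. The general part of 15.2 sets the criterion: "All tests will be two-tailed, and a p-value of 5% or less will be considered statistically significant".

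For categorical variables, the general part also plans 95% confidence intervals for proportions by study arm. No interval for the difference between sides is planned, no acceptable excess is named, and no power is given for any safety comparison. Section 15.1 sizes the trial on efficacy alone: "The rationale for sample size was based on demonstrating a difference in change in pocket depth between the tested segments and the control".

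Safety is also described in other ways. Section 9.2 plans "analyzing the adverse events, their quantity, severity, duration and their connection to the studied device", and 15.2 adds individual listings and tables by system organ class, preferred term, treatment and seriousness.

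**The concern.** The split-mouth design gives the trial one concurrent, within-patient control for local reactions. The quantity of interest there is how many more patients have a local event on the gel side than on the untreated side, and how large that excess could plausibly be. The only between-side result that the plan asks for is a p-value from a test of equality, in a sample chosen for pocket depth.

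The sponsor's own expectation in section 3.2 is "It is therefore expected that treatment with Pocket-X Gel will present a high safety profile during the study". If that is right, the likely outcome is p > 0.05. A p-value above 0.05 from about 30 patients cannot separate a gel that adds no local events from one that adds them in one patient in ten. Without an interval for the difference, the report would have nothing that tells the reader which excesses remain possible.

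**Working it through.** **Inputs from the documents.** Section 15.1: 34 recruited, 27 expected to complete. Section 15.2: the intention-to-treat set is everyone treated at least once, so up to 34 patients; no separate safety set is defined. Test: chi-square or Fisher, two-sided 5%.

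**Assumptions, because the documents are silent.** One yes/no local event outcome per side per patient; independent sides; control-side rates of 0% to 20%; a 10-point excess as illustration.

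**1. The plan's own figure.** A paired t-test with effect size 0.5 and one-sided 0.05 has power 79.8% at n = 26 and 81.2% at n = 27; 27/0.8 = 33.75, rounded up to 34. Both stated figures reproduce. They concern pocket depth only.

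**2. How many gel-side events reach significance?** With no control-side events in 34 patients, two-sided Fisher gives p = 2 × C(34,k)/C(68,k).
- k = 5: 2 × 278,256/10,424,128 = 0.053.
- k = 6: 0.025.

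So six patients are needed. The exact (Clopper-Pearson) 95% interval for 5/34 is 5.0% to 31.1%.

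**3. Chance of missing a 10-point excess with Fisher.** When the control rate is 0%, power is the chance of six or more events from a binomial with n patients and rate 0.10: 0.119 at n = 34 and 0.047 at n = 27. For other control rates, the probabilities of all significant pairs of counts are summed.

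| Control vs gel rate | Missed, n = 34 | Missed, n = 27 |
|---|---|---|
| 0% vs 10% | 88% | 95% |
| 5% vs 15% | 87% | 93% |
| 10% vs 20% | 88% | 92% |
| 15% vs 25% | 89% | 92% |
| 20% vs 30% | 90% | 93% |

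Larger excesses are found more often. For gel rates of 15% and 20% against 0%, the miss rates are 60% and 30% at n = 34, and 79% and 54% at n = 27.

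**4. Sensitivity to the test and to independence.**
- Uncorrected chi-square at 0% vs 10% misses 55% (n = 34) and 72% (n = 27), but the expected counts there are below 5, where Fisher would normally be chosen.
- Within-patient correlation of 0.3 to 0.5 (control rates 5% to 20%) raises Fisher's miss rate to about 91% to 96% at n = 34 and 95% to 98% at n = 27.
- Exact McNemar, which respects the pairing, misses about 87% to 91% and 92% to 95%. For 5 discordant pairs to 0 its p-value is 2 × 0.5^5 = 0.0625. Correcting the pairing alone does not remove the problem.

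**5. What an interval would show.** If both sides have the same observed rate p, the approximate upper 95% limit for the difference (Wald, independent sides) is 1.96 × √(2p(1−p)/n).
- n = 34: 10.4, 14.3 and 19.0 points for p = 5%, 10% and 20%.
- n = 27: 11.6, 16.0 and 21.3 points.

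With no gel-side events, the exact two-sided 95% upper limit for the gel-side rate is 1 − 0.025^(1/n): 10.3% at n = 34 and 12.8% at n = 27.

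**The case against.** A reader might infer that the plan treats a non-significant test as proof of safety. The documents do not support that. Section 15.2 only labels results at or below 5% as statistically significant and sets no safety decision rule.

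Nor does safety rest on this test alone. In the five-versus-none example all five events would be listed, graded for severity and relatedness, and tabulated by treatment. Unexpected or serious events go to the sponsor whatever the test shows. To call this comparison half of the safety objective would be a weighting that section 4 does not give; it is one of two named comparators. These points stand.

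The planned intervals for proportions would, if applied to each side, already give the 5% to 31% for 5/34 and the 10.3% for 0/34. That stands in part. The phrase by study arm is unclear in a single-arm study, and two separate intervals still do not bound the paired difference.

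The miss rates depend on the unit of analysis. Section 15.2 does not name it for local events, and elsewhere speaks of pockets. Counting 68 quadrants or 102 pockets per side as independent would lower Fisher's miss rate at 0% vs 10% to 31% and 5%, and at 10% vs 20% to 71% and 55%. Those counts ignore clustering within patients, so they are not valid analyses, but they show that the figures must be given with their assumptions.

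Low power for adverse events is also ordinary in a study of this size. That is why the remedy is a different summary and not more patients.

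**Conclusion.** The point holds as a cheap improvement in method, not as a demonstrated wrong decision rule. The sole planned between-side analysis of local events is a test of equality that, under the patient-level assumptions stated, misses a 10-point excess about 87% to 95% of the time with Fisher at 27 to 34 patients. The rate falls to 55% only with uncorrected chi-square at n = 34 and a control rate near zero. The 10-point excess and the event rates are illustrations; the documents supply neither. What does not depend on them is that no interval for the gel-minus-control difference is planned, and that at this sample size non-significance says little about added local harm.

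**What to change.** In the safety part of 15.2:

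- Report the within-patient difference in the proportion of patients with a local adverse event, gel-treated minus untreated control segments, with a 95% confidence interval for paired proportions.
- Define the control segments to match the treated ones in number, for example the contralateral segments. Section 5.2 allows one or two treated quadrants against two or three untreated, so exposure could otherwise differ between sides.
- Base the side-by-side safety statement on that interval, including its upper limit, and not on the p-value.
- State that a non-significant test is not evidence that the gel adds no local adverse events.

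Optionally, note in 15.1 that zero gel-side events would exclude only rates above 10.3% (34 patients) or 12.8% (27 patients).

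The cost is SAP wording and one extra statistic from data already collected, with no more patients or visits. The safety statement will read less favourably than a bare p-value.

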5. STUDY DESIGN

5.1. OVERALL DESIGN

This study is a single arm, open-label, split-mouth study.

All enrolled participants will initially undergo root planing and scaling on the entire mouth. Following the completion of scaling and root planing, each participant will have one/two of his/her mouth segments (quadrants) treated with Pocket-X Gel. The contralateral segment(s) of the Pocket-X Gel-treated segment(s) will serve as control.

The study hypothesis is that patients treated with Pocket-X Gel following scaling and root planing will exhibit better periodontal pocket healing on their treated segment(s) than their untreated segment(s) as well as compared to data available in the literature concerning the efficacy of scaling and root planing.

The total duration of the study for each participant will be 6-7 months. The study will include a total of 5-7 visits, depending on the number of scaling and root planing sessions required,

based on the severity of each participant's periodontal disease. Follow-up visits will occur 4, 12 and 24 weeks after completion of scaling and root planing and first application of the studied device. Detailed description of each visit is provided under section 5.5 – Visits and Follow-Ups.

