12. ADVERSE EVENTS

During each visit, participants will be asked whether they experienced or experience any adverse events. In case that an adverse event has occurred, investigators will record all details of the event and will assess whether the event may be related to the studied device.

Any new pathologies observed by the investigators that did not exist at baseline or have worsened since baseline, will be considered adverse events and recorded accordingly.

Participants will be requested to report any serious adverse events immediately to the investigators, without waiting for the next visit.

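### The planned significance test of adverse-event incidence against published SRP studies has no comparability rule, so its p-value can mix device effect with differences in capture, follow-up and population.

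*Combined protocol and SAP*

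**What the plan says.** The design has no concurrent group of patients who receive SRP alone. Section 5.1 states: "This study is a single arm, open-label, split-mouth study".

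The safety part of section 15.2 plans two comparisons. For localized events, treated and untreated segments of the same patient are compared by chi-square or Fisher's exact test. The second comparison is external: "Adverse events will also be compared to adverse events reported during scaling and root planing studies, based on available literature". Its method follows directly: "Chi-square test or Fisher's Exact test (as is appropriate) will be used for comparison in incidence of events". The general rule earlier in section 15.2 applies to it: "All tests will be two-tailed, and a p-value of 5% or less will be considered statistically significant".

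Sections 4 and 9.2 also list the literature comparison as part of how safety is evaluated.

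On capture, section 12 has participants questioned about events at each visit and adds: "Any new pathologies observed by the investigators that did not exist at baseline or have worsened since baseline, will be considered adverse events". Section 5.1 gives 6–7 months in the study per participant, and Table 1 in section 5.5 places the follow-ups at 4, 12 and 24 weeks.

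No section names the SRP studies to be used for this purpose or says how they will be selected, how events will be matched, or how the result should be interpreted.

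**The concern.** Chi-square and Fisher's tests allow for sampling error between two independent groups. They do not allow for the groups having been observed in different ways. Published SRP studies may have asked about events more or less often, counted examiner findings differently, followed patients for longer or shorter, or enrolled different patients. Each of these can shift the observed incidence with no device effect, and the test would attribute the shift to treatment. A shift the other way could hide a real excess.

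The comparison matters most for events that are not localized. These have no within-mouth comparator, so the literature is the only comparison the plan offers for them. Safety is one of the two parts of the overall objective in section 4, so a p-value of this kind could find its way into a safety conclusion.

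**Working it through.** **The plan's own figure.** Section 15.1 says "A sample size of 27 will have 80% power to detect an effect size of 0.5 using a Paired t-test"; the level it sets there is 5%, one-sided. The noncentral-t calculation reproduces this: effect size 0.5, one-sided 0.05 and n = 27 give 81.2% power. The plan then adds: "Assuming ~20% dropout rate, 34 subjects will be recruited, in order to have 27 participants who complete the study". Check: 27 / (1 − 0.20) = 33.75, rounded up to 34. This sizing concerns pocket depth. No figure is given for any safety comparison.

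**Inputs for the safety check.**
- Trial patients: n = 34 (section 15.1), the most favourable case.
- Test: Fisher's exact, two-sided, 0.05 (section 15.2).
- Published patients m, and the observed incidences p (trial) and q (literature): not in the documents. They are assumptions, shown over a range.

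**Formula.** Let X ~ Bin(34, p) and Y ~ Bin(m, q) be independent. The rejection probability is the sum, over all pairs (x, y) whose two-sided Fisher p-value is at most 0.05, of P(X = x) × P(Y = y). The enumeration is exact.

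**No device effect; observed rates differ only through capture, follow-up or population.**

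| Observed rate, trial v literature | Share captured in literature (q/p) | m = 34 | m = 100 |
|---|---|---|---|
| 20% v 20% | 1 | 2.4% | 3.7% |
| 20% v 15% | 0.75 | 4.4% | 9.8% |
| 30% v 20% | 0.67 | 9.9% | 20.9% |
| 30% v 15% | 0.50 | 22.3% | 44.8% |
| 30% v 10% | 0.33 | 43.8% | 73.8% |

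With equal capture the test keeps below its nominal 5%. The excess comes entirely from unequal observation. It grows with the size of the literature sample: at 30% v 10% and m = 300 the figure is 82.6%.

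**Real device effect, equal capture.** For a true doubling from 10% (literature) to 20% (trial), Fisher's test rejects 12.2% of the time at m = 34, 29.9% at m = 100 and 36.8% at m = 300.

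**Real device effect, masked.** Suppose the true rate doubles from 20% to 40% but the trial captures only half as many of its events as the literature does. Both observed rates are then 20%, and rejection is 2.4–3.7% for m = 34 to 300.

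**What 34 patients can exclude.** With 0 events in 34, the upper 95% limit is 1 − 0.05^(1/34) = 8.4% (one-sided) or 1 − 0.025^(1/34) = 10.3% (two-sided). With 3 events (8.8%) the exact two-sided interval is 1.9% to 23.7%. With 7 events (20.6%) it is 8.7% to 37.9%.

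**The case against.** Several points on the other side stand.

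- **Direction is not shown.** A reader might infer that this trial captures events more closely than published SRP studies and so will raise false alarms. The documents do not support that. They say nothing about capture in those studies, and the trial's own post-treatment questioning takes place at only three follow-ups, with gaps of about 8 and 12 weeks that rely on recall.
- **Size is not known.** The 74% belongs to a threefold gap in observed rates and 100 published patients. With a modest gap, the rejection rate is near or moderately above 5%.
- **Low power is not peculiar to this test.** It follows from having 34 patients. A descriptive report has the same imprecision, although an interval makes it visible.
- **Nothing hangs on the p-value.** The comparison is supplementary, and no success criterion, decision rule or stopping rule uses it. A reader might infer that non-significance will be taken as proof of safety, but no section says so.
- **Part of the remedy is already planned.** Section 15.2 calls for 95% confidence intervals for proportions of categorical variables, individual listings and tables of events, and a within-mouth comparison for localized events.

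These points limit the strength of the concern without removing it. The plan still prescribes a significance test whose result cannot be attributed to the device. The lack of a decision rule is also a reason why dropping it costs little.

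**Conclusion.** The concern holds in this form: an unadjusted two-sided 5% test against unspecified literature yields a p-value that can mix device effect with differences in capture, follow-up and population, in either direction.

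With no device effect and 34 to 100 published patients, false rejection runs from about 4–10% (20% v 15%) through 10–21% (30% v 20%) to 44–74% (30% v 10%). A true doubling from 10% to 20% is found about 30% of the time against 100 published patients, so non-significance could not support a claim of safety. All rates and literature sample sizes here are assumptions; only the 34 patients, the test and its level come from the plan. The stronger statement, that the test will give false signals or will falsely reassure, goes beyond what the documents show.

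The change should be made. It is modest in weight because the comparison is supplementary, and its value is greatest for events that are not localized.

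**What to change.** In section 15.2, delete the chi-square or Fisher's test against the literature. Replace it with incidence and an exact 95% confidence interval for each event type, set beside the published range, with each source's follow-up and method of event capture stated and no p-values. Say explicitly that for non-localized events this is descriptive context only. The literature references in sections 4 and 9.2 can stay if they are worded to match.

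Base comparative safety for localized events on the within-mouth contrast. Section 15.2 currently tests that contrast with chi-square or Fisher's test as well, which treats segments of one patient as independent. Use a method that respects the pairing, for example an exact McNemar test at patient level (event on the treated side only against event on the control side only).

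The cost is SAP wording, with no added patients, visits or data. The downside is that there will be no formal test against the literature.
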